2.4 Interventions

Multidisciplinary group

Patients randomized in the multidisciplinary group will receive their first sleep clinic evaluation with a specifically trained clinical nurse. For the past five years, a clinical nurse has been attached to the IUCPQ-UL sleep clinic. Her training enables her to complete the follow-up of patients treated with CPAP with a special attention to observance issue, identification and advices regarding any side effects patients may report. Before initiating consultation with patients as needed in this study, a specific training will be performed. Reference documents on diagnostic and therapeutic options will be selected by the respirologist in charge of the sleep clinic and given to the clinical nurse for instructions. She will also have a period of observation in the Ear Nose and Throat clinic and in the sleep laboratory for basic training regarding the completion and scoring of cardio-respiratory recordings by our sleep laboratory technicians. The clinical nurse will then complete her training assisting at the consultations of the respirologist at the sleep clinic's. The minimal duration of this observation period will be 1 month but could be extended if the nurse, the sleep clinic's physician or the principal investigator deemed it necessary.

After completion of the different steps of the training program, the clinical nurse will initially evaluate 2 patients per clinic and progressively increase to 5 patients per clinic. After complete evaluation of the patient, including questionnaire, physical and ENT examination, cardio-respiratory recording analysis and therapeutic discussion with the patient, the patient case will be discussed with the sleep clinic's appointed respirologist to determine the final treatment plan and/or the need for complementary investigations if required. Follow-up will be ensured by the clinical nurse with discussion with the physician if necessary.

Physician directed care group

Patient randomized in the physician directed care group will receive their first sleep clinic evaluation with a respirologist trained in sleep-disordered breathing disorders' evaluation and treatment. The physician will direct the questionnaire and physical examination, perform analysis of the cardio-respiratory recording and determine the treatment plan or additional complementary investigations, if necessary. Follow-up will be ensured by the clinical nurse of the sleep clinic.

2.5 Study outcomes and follow-up

Primary outcome: to assess the non-inferiority of a nurse-based compared with physician-based evaluation in the sleep clinic on:

1- Improvement in symptoms based on the Epworth Sleepiness Scale (ESS) which ranged from 0 to 24 points. Higher values are associated with increased sleepiness.

2- Quality of life as assessed by the Quebec quality of life questionnaire which is a questionnaire developed to assess health-related quality of life in patient with obstructive sleep apnea.³ It has 32 items scored on a 7 points Likert scale, providing a quality of life score for five different domains (with 4 to 7 items per domain):

- 1- Hypersomnolence;
- 2- Diurnal symptoms ;
- 3- Nocturnal symptoms;
- 4- Emotions;
- 5- Social interactions.

The lower the score, the higher the impact on the affected domain. Minimal clinically important difference differs for each domain. Lacasse et al. defined this value as such : hypersomnolence, 1.8; diurnal symptoms, 2.0; nocturnal symptoms, 1.5; emotions, 1.1; social interactions, 2.5.^{REF3}

These outcomes will be assessed at a three and six months' time frame.

Secondary objectives: to assess the non-inferiority of nurse-based compared with physician-based evaluation in the sleep clinic on treatment adherence. Outcome assessment will differ according to the treatment option chosen:

- 1- Positive pressure treatment (number of hours used/night according to CPAP report)
- 2- Mandibular advancement device (patient's usage report)
- 3- Surgical treatment
- 4- Weight loss treatment (changes in weight)
- 5- Positional therapy (proportion of time spent supine at baseline and at control cardio-respiratory recording)
- 6- Observation

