2.6 Data extraction

[name] will be responsible of data extraction through the digital patient files. Baseline demographic and anthropometric data, randomization group, baseline cardiorespiratory polygraphy, initial ESS and Quebec Quality of life questionnaire and retained treatment option will be extracted. Change in ESS and Quality of life as well as follow-up cardiorespiratory polygraphy examination will be reported at three and six months of follow-up. Any change in anthropometric data will also be NA & sleep apnea

evaluated.

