2.7 Statistical analysis

Statistical analysis for primary and secondary clinical end points will compare changes in scores at 3 months and six months between groups, using ANOVA. The lower limit of the two-sided 95% confidence intervals will be used to determine noninferiority. We anticipated an equal drop out rate (10 %) in the two study arms. All analyses were conducted in an intention-to-treat manner.

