2.7.1 Sample size

It was a priori determined, based on the reduction of ESS, that a sample size of 100 patients per group (200 patients total) was required for a power of 90%, assuming for a non-inferiority margin of 2.0 and a standard deviation of ESS changes of 2.0. The one-sided significance level (alpha) of the test was set at 0.025.

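### The adherence non-inferiority objective has no margin and no outcome defined for every randomised patient, so the confidence-limit rule in 2.7 cannot support a conclusion on it

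*Combined protocol and SAP*

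**What the plan says.** Section 2.5 makes non-inferiority of nurse-based to physician-based evaluation on adherence the secondary objective. It adds "Outcome assessment will differ according to the treatment option chosen" and lists six options: positive pressure (hours per night from the CPAP report), mandibular device (the patient's report of use), surgery, weight loss (weight change), positional therapy (share of time supine at baseline and at the control recording) and observation.

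Section 2.7 gives one method for primary and secondary end points: ANOVA of score changes at three and six months. The decision rule is "The lower limit of the two-sided 95% confidence intervals will be used to determine noninferiority", and the analysis set is "All analyses were conducted in an intention-to-treat manner". It also states "We anticipated an equal drop out rate (10 %) in the two study arms".

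The one analysis margin is in 2.7.1, where the sample size is based on Epworth score reduction, "assuming for a non-inferiority margin of 2.0 and a standard deviation of ESS changes of 2.0".

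On when treatment is chosen, 2.4 says that in the multidisciplinary arm, after the nurse's evaluation, "the patient case will be discussed with the sleep clinic's appointed respirologist to determine the final treatment plan". In the physician arm the physician settles the plan at the first evaluation. The nurse ensures follow-up in both arms. Section 2.6 states that the "retained treatment option will be extracted".

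**The concern.** A non-inferiority test needs an outcome, a population in which it is defined, and a margin fixed in advance. For adherence the plan gives several outcomes, none defined for all randomised patients, and no margin. A team that followed 2.7 to the letter would obtain a confidence limit and have nothing to set it against. If a margin were then chosen with the data in view, that choice could settle the answer.

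The second difficulty is the population. Patients are randomised to who performs the first evaluation, and the treatment option is decided at or after that evaluation. Comparing adherence among patients who received the same option therefore conditions on something the allocated evaluation may have influenced. That is not the intention-to-treat comparison that 2.7 promises. At stake is one secondary conclusion: a statement that nurse-based evaluation is non-inferior on adherence would have no prespecified basis.

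**Working it through.** The document states no adherence figure, so there is none to reproduce. The 100 per group in 2.7.1 concerns the Epworth score, and whether it follows from its inputs is a separate question.

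**1. Is there a margin?** The value 2.0 in 2.7.1 is in Epworth points. The domain values in 2.5 (1.1 to 2.5) are minimal clinically important differences for the quality-of-life questionnaire. Neither can be carried over to hours, weight or time supine. No other candidate appears.

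**2. Is there an outcome for every randomised patient?**

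| Option (2.5) | Measure | Better is |
|---|---|---|
| Positive pressure | hours per night | higher |
| Mandibular device | patient report, no scale given | higher |
| Surgery | none | – |
| Weight loss | weight change | lower |
| Positional therapy | share of time supine | lower |
| Observation | none | – |

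No composite, responder definition or lead measure links these rows. Because the direction of benefit differs, a single lower-limit rule would also need a sign convention, and none is stated.

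**3. Does the analysis variable fit?** The ANOVA is on changes. CPAP hours have no value before treatment, so no change can be formed.

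**4. Is the comparison intention-to-treat?** The order in 2.3 and 2.4 is consent, allocation, evaluation, treatment plan. A comparison within any option is therefore confined to a subset defined after randomisation.

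**5. Illustration: how a verdict depends on the margin.** From the document: 100 per arm and 10% dropout, so 100 × 0.9 = 90 completers per arm. Assumed: CPAP shares, SD of hours per night, and trial margins of 0.5 h and 1.0 h. Half-width of the 95% interval = 1.96 × SD × √(1/n₁ + 1/n₂). With shares of 60% and 80%, n = 54 and 72, and √(1/54 + 1/72) = 0.180. With 80% in both arms, n = 72 and 72, and √(2/72) = 0.167.

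| n compared | SD (h) | Half-width (h) | Zero difference, margin 0.5 h | Zero difference, margin 1.0 h |
|---|---|---|---|---|
| 54 and 72 | 1.5 | 0.53 | not shown | non-inferior |
| 54 and 72 | 2.0 | 0.71 | not shown | non-inferior |
| 54 and 72 | 2.5 | 0.88 | not shown | non-inferior |
| 72 and 72 | 1.5 | 0.49 | non-inferior | non-inferior |
| 54 and 72 | 3.0 | 1.06 | not shown | not shown |

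The first three rows show the same data passing or failing by choice of margin. The last two show that this is not so for every input.

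**6. Illustration: coverage.** At 60% and 80%, treatment choice leaves 40 + 20 = 60 of 200 randomised patients outside the CPAP comparison. Among completers it leaves (90 − 54) + (90 − 72) = 54 of 180.

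**7. Illustration: possible selection effect.** Suppose each arm gives CPAP to the top fraction p of patients on a ranking that correlates r with hours of use. Mean use among those selected is then μ + r × SD × φ(z_p)/p, where φ(z_p)/p = 0.644, 0.570, 0.424 and 0.350 for p = 0.60, 0.65, 0.75 and 0.80. At SD 2:
- 65% against 75%: 0.146 × 2 × r = 0.09 h (r = 0.3) to 0.15 h (r = 0.5).
- 60% against 80%: 0.294 × 2 × r = 0.18 h (r = 0.3) to 0.29 h (r = 0.5).
- Equal shares under the same rule, or r = 0: zero.

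**The case against.** The strongest reply is that part of this criticises an analysis the plan never describes. Section 2.7 says only that end points are compared between groups; it does not say that adherence will be compared within options. That is fair, and the intention-to-treat point is conditional on such a comparison. But listing a separate measure for each option leaves comparison within options as the most direct use, and no alternative is offered. The missing margin and missing common outcome do not depend on it.

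A reader might infer that adherence results will be biased by selection. The documents do not support that. A respirologist takes part in the treatment decision in both arms (2.4), and one eligibility filter applies to everyone (2.2). Nothing suggests that CPAP shares will differ. The effects of 0.09 to 0.29 h rest entirely on assumed shares, SD, correlation and ranking rule.

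A reader might also put the number outside the CPAP comparison at 200 − (54 + 72) = 74. That mixes in the 20 planned dropouts (10% of 200), who could lack follow-up data for any endpoint.

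Section 2.6 does not list CPAP-report hours or device use; for follow-up it says "Change in ESS and Quality of life as well as follow-up cardiorespiratory polygraphy examination will be reported at three and six months of follow-up" and adds anthropometric change. One might infer that adherence will go uncollected. But 2.5 names the CPAP report and the patient's report of use, and 2.6 does not call its list exhaustive. This is a gap in wording.

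Finally, surgery and observation may simply have no continuous measure of use, and a justified CPAP-hours margin would be cheaper than a new endpoint. Both are reasonable. Such a margin would supply half of what is missing, but the comparison would still cover only a subset chosen after randomisation.

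**Conclusion.** The point holds. As written, the rule in 2.7 cannot support an adherence non-inferiority conclusion: no adherence margin exists, no adherence outcome is defined for all randomised patients, the change-score analysis does not fit CPAP hours, and a comparison within an option is not intention-to-treat. This follows from the text alone and needs no assumed number.

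Its numerical size cannot be established, because the document gives no treatment mix, mean hours or SD. The interval widths, coverage counts and selection effects above are illustrations under assumed inputs. Whether comparison within options would be biased, and by how much, cannot be known from the document; the bias may be nil.

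The consequence is limited to one secondary objective. It would be wrong to infer that the trial's main result is undermined: the Epworth analysis and the sample size based on it are not affected by this adherence issue. The plan should be changed here, but the issue is not fatal to the trial.

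**What to change.** In 2.5 and 2.7:

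1. Compare the distribution of the retained treatment option between arms in all randomised patients, with a category for those with none recorded. This respects the randomisation.
2. Report CPAP hours and the other option-specific measures by arm with confidence intervals. Label them descriptive and not intention-to-treat, and draw no non-inferiority conclusion from them.
3. Keep an adherence non-inferiority claim only if one endpoint, defined for every randomised patient and with its own justified margin and direction, is prespecified before the data are seen. An adherent/not-adherent classification is one possibility. It must state how surgery, observation and dropout count, because treating any of them as adherent by default would let an arm's treatment mix drive the result.

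In 2.6, name CPAP-report hours and device use, to match 2.5.

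Step 1 costs wording and one table, since the option is already extracted. Step 2 costs wording and confirmation that two items planned in 2.5 are extracted. Step 3 is optional and costs more: a definition for each option and a defended margin. The real downside is that, without step 3, the secondary adherence comparison loses its non-inferiority conclusion.

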2.6 Data extraction

[name] will be responsible of data extraction through the digital patient files. Baseline demographic and anthropometric data, randomization group, baseline cardiorespiratory polygraphy, initial ESS and Quebec Quality of life questionnaire and retained treatment option will be extracted. Change in ESS and Quality of life as well as follow-up cardiorespiratory polygraphy examination will be reported at three and six months of follow-up. Any change in anthropometric data will also be NA & sleep apnea

evaluated.

2.7 Statistical analysis

Statistical analysis for primary and secondary clinical end points will compare changes in scores at 3 months and six months between groups, using ANOVA. The lower limit of the two-sided 95% confidence intervals will be used to determine noninferiority. We anticipated an equal drop out rate (10 %) in the two study arms. All analyses were conducted in an intention-to-treat manner.

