2. METHODS

2.1 Study Design Overview

This study is a randomized open label non-inferiority study. The research protocol was approved by the IUCPQ-UL research ethics committee. Patients are to provide written informed consent upon inclusion in the study.

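### The change-score ANOVA for ESS and quality of life leaves out the baseline score, which is already collected; adjusting for it would gain precision at no cost

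*Combined protocol and SAP*

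**What the plan says.** Section 2.7 states that the analysis of primary and secondary end points "will compare changes in scores at 3 months and six months between groups, using ANOVA". It names no covariate, and no other section provides for baseline adjustment. The decision rule in the same section is "The lower limit of the two-sided 95% confidence intervals will be used to determine noninferiority".

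The baseline values will be on file: section 2.6 says that "initial ESS and Quebec Quality of life questionnaire and retained treatment option will be extracted". Section 2.3 randomises 1:1 in blocks of twenty and does not stratify by baseline score.

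Section 2.7.1 gives the ESS planning inputs, "assuming for a non-inferiority margin of 2.0 and a standard deviation of ESS changes of 2.0", with a one-sided alpha of 0.025, and concludes "that a sample size of 100 patients per group (200 patients total) was required for a power of 90" per cent. On attrition, section 2.7 says "We anticipated an equal drop out rate (10 %) in the two study arms".

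**The concern.** A change score fixes the coefficient of baseline at 1. ANCOVA estimates that coefficient from the data, so its large-sample residual variance is never larger and is usually smaller. The unadjusted contrast also carries part of any chance difference between arms at baseline.

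Neither feature makes the ANOVA wrong. Over repeated randomisations it is unbiased and its error rate is correct. What is at stake is the width of the interval that decides non-inferiority, and how far one trial's result depends on the luck of the baseline draw. Both can be improved with data the trial already collects.

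**Working it through.** **Inputs from the documents.** ESS margin 2.0; SD of change 2.0; one-sided alpha 0.025; power 90%; 100 per group (section 2.7.1); 10% dropout (section 2.7), hence 90 evaluable per arm.

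**Assumptions, not in the documents.** Baseline ESS SD s0 of 4 to 5; follow-up SD s1 equal to s0 (relaxed below); true difference zero unless stated.

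**The plan's own figure.** With margin 2.0 and SD 2.0, the normal formula gives n = 2 × [2.0 × (1.960 + 1.282) / 2.0]² = 21.0, so 22 per group (23 with the t distribution), or 25 after 10% dropout. The stated 100 does not reproduce. If the margin of 2.0 and a zero true difference are kept, 90% power corresponds to an SD of change of 4.34 at 100 per group or 4.12 at 90. That mismatch is a separate point; here it only motivates a second scenario with SD of change 4.0.

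**Formulas** (rho is the correlation of baseline with follow-up)

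- Var(change) = s0² + s1² − 2·rho·s0·s1
- Residual variance under ANCOVA = s1²(1 − rho²)
- Share of a baseline difference carried into the change contrast = 1 − rho·s1/s0
- With s1 = s0 = s: rho = 1 − SDchange²/(2s²), SE ratio (ANCOVA to ANOVA) = √[(1 + rho)/2], carry-over = 1 − rho
- Shift from a baseline imbalance at its 95% limit = 1.96 × s × √(2/90) × (1 − rho)

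**Results at 90 per arm, equal variances**

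| SD of change | s | rho | SE ratio | 95% half-width, ANOVA → ANCOVA | Power, ANOVA → ANCOVA | Shift (ESS points) |
|---|---|---|---|---|---|---|
| 2.0 | 4 | 0.875 | 0.968 | 0.588 → 0.570 | >99.9% → >99.9% | 0.146 |
| 2.0 | 5 | 0.92 | 0.980 | 0.588 → 0.576 | >99.9% → >99.9% | 0.117 |
| 4.0 | 4 | 0.50 | 0.866 | 1.177 → 1.019 | 91.6% → 97.1% | 0.58 |
| 4.0 | 5 | 0.68 | 0.917 | 1.177 → 1.079 | 91.6% → 95.4% | 0.47 |

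Against the margin of 2.0, the shift is 6–7% at SD 2.0 and 23–29% at SD 4.0.

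**Unequal variances.** Solve the first formula for rho. For s0 = 4, s1 = 3.6 and SD of change 2.0: rho = (16 + 12.96 − 4)/(2 × 4 × 3.6) = 0.867, and the SE ratio is 3.6 × √(1 − 0.867²)/2.0 = 0.898. The full set of SE ratios is:

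| SD of change | s0 | s1/s0 = 0.9 | s1/s0 = 1.1 |
|---|---|---|---|
| 2.0 | 4 | 0.898 | 0.999 |
| 2.0 | 5 | 0.899 | 0.998 |
| 4.0 | 4 | 0.804 | 0.919 |
| 4.0 | 5 | 0.855 | 0.963 |

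**Other correlations.** If rho is instead set to 0.3–0.8 at SD of change 2.0, the half-width (normal quantile) falls from 0.584 to 0.471–0.554, which is 5–19% narrower. With equal variances this needs a baseline SD of 2.0/√[2(1 − rho)], or 1.7–3.2, smaller than the 4–5 assumed above.

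**Validity.** In 20,000 simulated trials per setting, at 90 per arm and with the true difference at the margin, false non-inferiority occurred in 2.3–2.4% with ANOVA and 2.2–2.6% with ANCOVA over the four settings of the first table (nominal 2.5%). The mean estimate was 2.00 with both models.

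**The case against.** On the documents' own ESS inputs nothing would change: the half-width moves from 0.59 to 0.57–0.58, power exceeds 99.9% either way, and the ANOVA is valid. On that reading the choice of model is close to a matter of preference. This stands for the expected ESS decision at SD 2.0, and is why the point is ranked as a free improvement only.

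The SD of 4.0 is also just one way to explain 100 per group. A margin of 1.0, or a true difference of 1.0 against the nurse arm, each with SD 2.0, gives 85 per group, or 95 with dropout. The documents do not say which input is off, so this stands too. With SD 2.0 and a true difference of 1.0, power at 90 per arm goes from 91.6% to 92.6–93.1%: a smaller gain, but still a gain.

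The size rests on assumed values and can be close to nil: 0.1–0.2% at SD 2.0 if the follow-up SD is 10% above baseline. That is correct. Calling the ANOVA valid also presumes sound allocation and dropout unrelated to baseline score. If either failed, adjustment could remove some bias as well, which would strengthen the case for it.

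Finally, section 2.8 puts study completion in December 2018, and the documents do not show whether outcomes have already been compared by arm. If they have, a change of primary model would be post hoc.

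**Conclusion.** The point holds as a free improvement. No baseline covariate is planned, the baseline scores are collected, and adjustment would add precision without repairing any fault of validity. At the stated SD of change of 2.0 the ESS interval is 2–3% narrower (0.1–10% if the follow-up SD differs from baseline by 10% either way), with no change in the expected decision. At an assumed SD of 4.0 it is 8–13% narrower (4–20% on the same variation), and the risk of missing non-inferiority when the arms are truly equal falls from about 8% to 3–5%. The omission is certain. The size depends on an assumed baseline SD of 4–5 and the correlation that follows from it. For the five quality-of-life domains the documents give no SD or correlation, so the gain there cannot be quantified.

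**What to change.** In section 2.7, state that change in ESS and in each quality-of-life domain, at 3 and at 6 months, is analysed by ANCOVA on arm plus the baseline value of the same score, and that the non-inferiority confidence limit is taken from the adjusted arm difference. Keep the ANOVA for secondary end points with no baseline value, such as CPAP hours per night. The same wording can extend to weight change and time spent supine, which do have one.

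The cost is a change of SAP wording and one degree of freedom per model, with no new data and no extra patients. The condition is timing: section 2.1 says "This study is a randomized open label non-inferiority study", so the wording should be fixed and dated before outcomes are compared by arm. If that moment has passed, keep the ANOVA as primary and report the adjusted analysis as a sensitivity analysis, labelled post hoc.

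### The ANOVA on change scores has no missing-data method, so the claimed intention-to-treat analysis defaults to observed cases, with bias of unknown direction

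*Combined protocol and SAP*

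**What the plan says.** Section 2.7 names one method for the primary and secondary endpoints: to "compare changes in scores at 3 months and six months between groups, using ANOVA". The decision rule follows: "The lower limit of the two-sided 95% confidence intervals will be used to determine noninferiority". On attrition the section says "We anticipated an equal drop out rate (10 %) in the two study arms", without giving the time point to which the 10% applies. On the analysis set it says "All analyses were conducted in an intention-to-treat manner".

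Section 2.7.1 sets 100 patients per group, "assuming for a non-inferiority margin of 2.0 and a standard deviation of ESS changes of 2.0", and adds "The one-sided significance level (alpha) of the test was set at 0.025".

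The document does not define the intention-to-treat set or give a rule for a missing 3- or 6-month score. It plans no missing-data sensitivity analysis. Section 2.6 describes extraction of scores from the digital patient files but no way of recovering those that are absent.

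**The concern.** Intention-to-treat means that all randomised patients count in their assigned arm. An ANOVA of change needs a follow-up score from each patient it includes. With dropout expected, the two statements in section 2.7 cannot both hold for all randomised patients unless a missing-data method is added, and none is.

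This is a non-inferiority trial, open label (section 2.1), with patient-reported questionnaires as primary outcomes (section 2.5). If nurse-arm patients who are lost do worse than lost physician-arm patients, the observed difference shrinks and a false claim of non-inferiority becomes more likely. Equal dropout rates do not prevent this, because bias depends on the outcomes of those who leave as well as on their number. Two smaller losses follow from the same method: the 6-month comparison makes no use of 3-month scores from patients missing at 6 months, and baseline sleepiness is not used as a covariate.

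**Working it through.** **Inputs from the plan.** Margin 2.0 ESS points, SD of change 2.0, one-sided alpha 0.025, 100 per group (section 2.7.1); 10% dropout per arm (section 2.7).

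**Assumptions.** SD 4.0 as an alternative; the values of d below; the 10% applies to the visit analysed.

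**The plan's own figure.** With a true difference of 0 (none is stated), n per arm = 2 × 2.0² × (1.960 + 1.282)² / 2.0² = 21.01, so 22, or 25 after 10% dropout. The stated 100 is not reproduced; at 100 per arm power exceeds 99.9%. That is a separate matter. Here it shows only that losing 10% is not a power problem at the stated SD: 90 per arm still gives more than 99.9%. The issue is bias.

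**Patients without a score.** 0.10 × 100 = 10 per arm, 20 of 200. If the 10% is cumulative to 6 months, fewer are missing at 3 months.

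**Bias.** Let the deficit be physician-arm improvement minus nurse-arm improvement. Let d be how many points larger the deficit is among dropouts than among observed patients. Then

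all-randomised deficit = 0.9 × observed + 0.1 × (observed + d) = observed + 0.1d.

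With the all-randomised deficit at the margin, the observed deficit is 2.0 − 0.1d.

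**False non-inferiority rate.** SE = SD × √(2/90), which is 0.298 at SD 2.0 and 0.596 at SD 4.0. The rate is the probability that a noncentral t variable with 178 degrees of freedom and noncentrality 0.1d/SE exceeds 1.973.

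| d | Observed deficit | Rate, SD 2.0 | Rate, SD 4.0 |
|---|---|---|---|
| −2 (physician-arm dropouts worse) | 2.2 | 0.4% | 1.1% |
| 0 (dropouts equally bad in both arms) | 2.0 | 2.5% | 2.5% |
| 2 (nurse-arm dropouts worse) | 1.8 | 9.8% | 5.2% |
| 4 (nurse-arm dropouts worse) | 1.6 | 26.6% | 9.8% |

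A normal approximation gives nearly the same results: 9.9% and 26.8% for d = 2 and 4 at SD 2.0.

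**Unequal rates.** If dropout were 15% in the nurse arm and 5% in the physician arm, with dropouts 2 points worse in both, the bias would be 0.15 × 2 − 0.05 × 2 = 0.2. That is the same bias as in the d = 2 row.

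**Cost of the penalised analysis.** The shift is 0.10 × 2.0 = 0.2. At a true difference of 0, using the SE for 90 per arm, (2.0 − 0.2)/0.298 = 6.04, so the chance of showing non-inferiority stays above 99.9% at SD 2.0. At SD 4.0 the ratio falls from 2.0/0.596 = 3.35 to 1.8/0.596 = 3.02, and the chance from about 92% to 85%. These figures leave out any extra variance from imputation and any precision gained from baseline adjustment.

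**The case against.** The strongest reply is that this is silence, not a declared method. Section 2.7 does not say that patients with missing scores are dropped, does not say that each visit has its own ANOVA, and does not rule out imputation beforehand. That is correct. A reader might infer that the plan prescribes separate ANOVAs and is really a completers analysis; the text supports neither. Visit-by-visit ANOVA would be an available-case analysis: a patient seen only at 3 months counts at 3 months, and one who stops treatment but returns the questionnaire stays in the assigned arm. The point does not depend on the word separate, however, because a repeated-measures ANOVA would also lose patients, possibly more.

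The second reply is that the direction of bias is assumed. This also stands. Nothing in the document shows that patients doing badly are likelier to leave, or that this differs by arm. Section 2.4 gives follow-up to the clinical nurse in both arms, which makes arm-specific attrition less obvious. The 26.6% is a stress case: at d = 4 the nurse-arm deficit is 1.6 points among observed patients and 5.6 among dropouts.

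The third reply is that a mixed model does not by itself repair the problem. It omits patients with no follow-up score and assumes missing at random, so it need not remove the bias computed above. That is why the sensitivity analysis is an essential part of the remedy.

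What none of this answers is that the plan expects missing scores, claims intention-to-treat, and names a method that cannot use a patient without a follow-up score.

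**Conclusion.** The point holds in a limited form. Followed as written, section 2.7 yields an observed-case analysis that leaves out up to about 10 patients per arm, which is not the intention-to-treat analysis it claims. The bias could inflate the false non-inferiority rate, leave it at 2.5% or lower it. Over the range shown (d from −2 to 4) that rate runs from 0.4% to 26.6% at the stated SD, and from 1.1% to 9.8% at SD 4.0. These figures rest on the assumed d values and on 10% missing at the visit analysed. The document does not support the stronger conclusion that the analysis will favour the nurse arm. It is a gap that should be closed, at little cost.

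**What to change.** Replace the ANOVA on change scores with one mixed model for repeated measures with arm, visit, arm-by-visit interaction and baseline score. Include every randomised patient with any post-baseline score, in the assigned arm, and report the 3- and 6-month contrasts with 95% confidence intervals.

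Define the intention-to-treat set as all randomised patients. Add a sensitivity analysis on that set which imputes missing scores in both arms and makes the imputed nurse-arm ESS values worse by the margin, 2.0 points. Call ESS non-inferiority robust only if it survives. The penalty corresponds to the d = 2 row above, so it does not cover the d = 4 case. It is expressed in ESS points, because section 2.7.1 states its margin for ESS only.

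The cost is plan wording and some analysis time; no new data are needed. The downside is the 0.2-point shift in the sensitivity analysis: negligible at SD 2.0, and about 7 percentage points of power (92% to 85%) at an assumed SD of 4.0.
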